Impairment of host defense.	
Host defense has not been studied directly in nonclinical studies. However, data in nonclinical species have not identified an increased risk of infection with danirixin. Nonclinical studies in mice and ferrets with two CXCR2 antagonists in the same chemical class as danirixin have not shown an increase in infections in challenge models (e.g., influenza viral load). Secondary bacterial infections after viral infection have not been directly evaluated in nonclinical studies.
 
The data from clinical studies including healthy participants, COPD and influenza patients thus far show no evidence that participants taking danirixin have an increased infection rate compared with participants taking placebo.
 
Neutropenia has been reported in clinical trials of other CXCR2 antagonists. No instances of neutropenia have been reported in nonclinical studies with danirixin. In healthy volunteer studies and a phase 2a study in patients with Influenza (GSK Study
	
Monitoring of neutrophil count.
 
Stopping criteria: in participants with a confirmed absolute neutrophil count $\leq 0.5 \times 10^9/L$ product will be discontinued and neutrophil count will be monitored until return to normal. Participants may be restarted on study treatment as detailed in Appendix 9.
 
Ongoing assessment of AE/SAEs related to infection.
 
Closely monitor, collect information on and characterize infection events such as pneumonia, and use adjudication as appropriate.

Investigational Product (IP) [Danirixin, GSK1325756]		
Potential Risk of Clinical Significance	Summary of Data/Rationale for Risk	Mitigation Strategy
	
201682, GlaxoSmithKline Document No. 2014N205875_00), decreased neutrophil counts have been observed in subjects receiving either placebo or danirixin; no instances of danirixin-related neutropenia have been reported in clinical studies to date. In healthy subjects, the data are confounded by the observation of low neutrophil counts before dosing or at follow-up, and were not dose-related, while in patients with influenza, neutrophil counts recovered while receiving danirixin, coincident with resolution of the viral infection. There have been no reports of neutrophil count decreases below the lower limit of normal in patients with COPD who were treated with danirixin for one year. These data support the conclusion that a causal association of neutropenia with danirixin cannot be definitively established.
	

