## 11. BIOMARKER ANALYSES

C-reactive protein and fibrinogen data will be summarized in the same way as laboratory data. Summary tables and boxplots for each treatment by visit (including screening, baseline, Day 84 and Day 168) will be generated for the mITT populations and also for the subset of subjects who have an event in the 'Infective pneumonia' SMQ.

Exploratory biomarker analysis will be the subject of a separate RAP.

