**NOTES :**

- The treatment phase definitions specified in Section 14.4.1.4 will be used and only assessments within the on-treatment period will be considered in assessment of minimum/maximum/worst-case post-baseline.
- Assessment of minimum/maximum/worst-case post-baseline will include on-treatment data from scheduled, unscheduled and study treatment discontinuation visits (if applicable)

Laboratory Parameters
------------------------------

General
----------------

- NQ laboratory results will be treated as missing in summary displays. However, the results will be listed as received (e.g. '<x' or '>x').
- If numeric laboratory results are missing but a character result has been recorded, ie. <X, (the numeric part of the character value)/2 will be used to assign the PCI ranges.
- A 'worst case post-baseline' change classification will be derived, in which participants will be counted in the 'to low' and 'to high' categories if they reported a change from an 'in range' baseline to a value below or above the PCI criteria (respectively) at any scheduled or unscheduled on-treatment visit. Participants who did not report a change to a value outside the PCI criteria at any visit after the start of study treatment will be counted in the 'to w/in range or no change' category.

Multiple Measurements for On-Treatment Visits for Safety
---

- Participants having both high and low values relative to PCI criteria at post-baseline visits for safety parameters will be counted in both the high and low categories of the "worst case post-baseline" row of related summary tables.

ECG		
General		

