## 14.8. Appendix 8: Values of Potential Clinical Importance

### 14.8.1. Laboratory Values

The following table identifies a range of potential clinical importance (PCI) for each laboratory analyte. Limits with an 'x' are multipliers of the central laboratory normal range. Values above and below this range will be considered of PCI.

Hematology Analyte (units)	Effect	COPD Patients	
		Low	High
Platelet Count (x10  /L)		0.90x	1.10x
Red Blood Cell Count (x10  /L)		0.93x	1.07x
White Blood Cell Count (x10  /L)		0.70x	1.60x
Reticulocyte Count (%)			>4%
Hemoglobin (g/L)	Males	0.85x	1.20x
	Females	0.85x	1.20x
Hematocrit (Ratio of 1)	Males	0.50x	1.30x
	Females	0.50x	1.30x
MCV (fL)		0.25x	2.00x
MCH (pg)		0.85x	1.20x
MCHC (g/dL)		0.85x	1.10x
Neutrophils (%)		0.65x	1.50x
Lymphocytes (%)		0.80x	1.20x
Monocytes (%)		0.80x	1.60x
Eosinophils (%)			2.00x
Basophils (%)			5.00x

Note: Multipliers are identified by "x", otherwise actual comparison values are provided with units.

Chemistry Analyte	Effect	COPD Patients	
		Low	High
BUN (mmol/L)		0.70x	1.60x
Creatinine (μmol/L)			1.30x (or >27 μmol/L increase from baseline)
Glucose fasting (mmol/L)		<0.6x	>4x
Sodium (mmol/L)		0.80x	1.15x
Potassium (mmol/L)		0.75x	1.30x
Chloride (mmol/L)		0.90x	1.10x
Bicarbonate (mmol/L)		<18 mmol/L	>32 mmol/L
Calcium (mmol/L)		0.85x	1.08x
GGT (U/L)		0.85x	1.10x
Uric Acid (mg/dL)	Males	<2.1 mg/dL	>8.5 mg/dL
	Females	<2.0 mg/dL	>7.0 mg/dL
Albumin (mmol/L)		0.90x	1.50x
Total Protein (mg/dL)			1.25x

Note: Multipliers are identified by “x”, otherwise actual comparison values are provided with units.

Liver Function Test Analyte	Effect	PCI Range	Unit
ALT/SGPT	High	≥ 3x ULN	U/L
AST/SGOT	High	≥ 3x ULN	U/L
Alkaline Phosphatase	High	≥ 2x ULN	U/L
Total Bilirubin	High	≥ 2x ULN	μmol/L
Direct Bilirubin	High	≥ 2x ULN	μmol/L
Total Bilirubin + ALT	High	≥ 2x ULN Total Billirubin + ≥ 3x ULN ALT	μmol/L  U/L

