3.6	3.13	mITT	AE1/AE3	Summary of On-treatment Adverse Events Leading to Permanent Discontinuation of Study Treatment or Withdrawal from Study by [System Organ Class and] Preferred Term	IDSL Use AE1 for interim with text in [] in title Use AE3 for final reporting with text in [] omitted.	StInt, SAC
3.7	3.14	mITT		Summary of On-treatment Adverse Events of Special Interest		StInt, SAC
	3.15	mITT		Summary of On-treatment Pneumonia (AE and SAE) by ICS	AE and SAE Subjects who have an event in the 'Infective pneumonia' SMQ By subjects receiving ICS for at least 7 days at the time on pneumonia onset.	Post SAC
Laboratory: Chemistry						
3.8	3.16	mITT	LB1	Summary of Chemistry Changes from Baseline	ICH E3, include change from baseline of min/max value	StInt, SAC
3.9	3.17	mITT	LB17	Summary of Worst Case Chemistry Results by Potential Clinical Importance Criteria	ICH E3	StInt, SAC
Laboratory: Hematology						
3.10	3.18	mITT	LB1	Summary of Hematology Changes from Baseline	ICH E3, include change from baseline of min/max value	StInt, SAC
3.11	3.19	mITT	LB17	Summary of Worst Case Hematology by Potential Clinical Importance Criteria	ICH E3	StInt, SAC

Safety: Tables						
StInt No.	SAC No.	Population	IDSL / Example Shell	Title	Programming Notes	Deliverable [Priority]
Laboratory: Hepatobiliary (Liver)						
3.12	3.20	mITT	LIVER1	Summary/Listing of Liver Monitoring/Stopping Event Reporting	IDSL – if there are very small number of events this summary will be replaced with a listing. Table title to be determined by content.	StInt, SAC
3.13	3.21	mITT	LIVER10	Summary/Listing of Hepatobiliary Laboratory Abnormalities	IDSL – if there are very small number of events this summary will be replaced with a listing. Table title to be determined by content.	StInt, SAC
ECG						
	3.22	mITT	EG1	Summary of ECG Findings	IDSL, include min/max value	SAC
	3.23	mITT	EG2	Summary of Change from Baseline in ECG Values by Visit	IDSL include change from baseline of min/max value	SAC
3.14	3.24	mITT	EG10	Summary of Maximum QTcF Values Post-Baseline Relative to Baseline by Category	IDSL	StInt, SAC
3.15	3.25	mITT	EG11	Summary of Maximum Increase in QTcF Values Post-Baseline Relative to Baseline by Category	IDSL	StInt, SAC
Vital Signs						
	3.26	mITT	VS1	Summary of Change from Baseline in Vital Signs	ICH E3, include change from baseline of min/max value	SAC
	3.27	mITT	VS7	Summary of Worst Case Vital Signs Results by Potential Clinical Importance Criteria	IDSL	SAC

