## 14.11.11. Pharmacokinetic / Pharmacodynamic Figure

Pharmacokinetic / Pharmacodynamic: Figures					
SAC No.	Population	IDSL / Example Shell	Title	Programming Notes	Deliverable [Priority]
5.1	PK		Scatter plot of PD endpoint versus Danirixin Concentration (Trough)	CAT Total Score Include Placebo imputed as DNX conc=0ng/mL, include DNX conc=NQ imputed as LLOQ/2, where LLOQ=5ng/mL By Day Different symbol for each treatment	Post SAC
5.2	PK		Scatter plot of Safety versus Danirixin Concentration (Trough)	Blood Neutrophil Count and C-reactive Protein (CRP) Highlight subjects with an on-treatment event in the 'Infective pneumonia' SMQ. Add footnote 'Note: Pneumonia may have occurred at any time during the study' Include Placebo imputed as DNX conc=0ng/mL, include DNX conc=NQ imputed as LLOQ/2, where LLOQ=5ng/mL By Day Different symbol for each treatment	Post SAC
5.3	PK		Quartile plot of Danirixin Concentration versus PD endpoint	CAT Total Score	Post SAC
5.4	PK		Quartile plot of Danirixin Concentration versus Safety endpoint	Blood Neutrophil Count and C-reactive Protein (CRP)	Post SAC

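### Neutrophils are screened for clinical importance only as a percentage, so moderately low absolute counts can go unflagged; dropping '<x' CRP results is a smaller gap

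*SAP*

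**What the plan says.** **Neutrophils.** Protocol Section 3.3.1 gives the reason for watching them: "Neutropenia has been reported in clinical trials of other CXCR2 antagonists". Section 10.5.4.3 names them among the key safety endpoints of the strategic interim. Every protocol rule on them is an absolute count:

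- below 1.5 ×10^9/L excludes (Section 6.2, criterion 5);
- a confirmed count at or below 0.5 suspends dosing (Section 8.1.3);
- at least 1.5 is required for restart, and a fall below 1.0 after restart has its own consequence (Appendix 9).

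SAP Section 14.8.1 opens with "The following table identifies a range of potential clinical importance (PCI) for each laboratory analyte". Its only neutrophil row is a percentage, at 0.65x low and 1.50x high. The total white cell (WBC) row is a count, at 0.70x low. The multipliers apply to central laboratory limits that the SAP does not state. These criteria drive the table titled "Summary of Worst Case Hematology by Potential Clinical Importance Criteria" (Table 3.19) and haematology Listings 28 and 30.

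**NQ results.** SAP Section 14.6.4 states "NQ laboratory results will be treated as missing in summary displays". It also says that such results are listed as received, and that half the numeric part of a '<X' result "will be used to assign the PCI ranges". Section 11 adds: "C-reactive protein and fibrinogen data will be summarized in the same way as laboratory data". Neither CRP nor fibrinogen has a PCI row. In the PK/PD figures (Section 14.11.11) the instruction for drug concentrations is "include DNX conc=NQ imputed as LLOQ/2".

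**The concern.** A percentage need not fall when neutrophils and total white cells fall together. A participant can therefore have an absolute count below a protocol threshold and still sit inside the percentage criterion. If the WBC criterion is also met, Table 3.19 counts that participant as within range or unchanged for both analytes. If no other haematology analyte is flagged, the participant is also absent from Listings 28 and 30. The SAP has both a stopping-event display and a laboratory-abnormality display for the liver (Tables 3.20 and 3.21), but no counterpart for neutrophils. The reader of the final report would then have no count, by arm, of participants below the levels the protocol itself uses.

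For CRP, a '<x' result is known to be low. Deleting it shifts the summary upward, and more so in an arm whose CRP has been lowered. A true reduction would look smaller than it is.

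**Working it through.** The plan states no figure on either point, so there is nothing to reproduce. Both checks rest on assumed inputs.

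**1. Lowest absolute count that passes both flags**

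Inputs: multipliers 0.70 (WBC) and 0.65 (neutrophil %) from SAP Section 14.8.1. Assumed lower limits of normal (LLN): WBC 3.5 to 4.5 ×10^9/L, neutrophils 38% to 50%.

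Lowest unflagged count = (0.70 × WBC LLN) × (0.65 × neutrophil % LLN / 100).

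| WBC LLN | WBC cut | 38% LLN (cut 24.7%) | 40% (26.0%) | 45% (29.25%) | 50% (32.5%) |
|---|---|---|---|---|---|
| 3.5 | 2.45 | 0.61 | 0.64 | 0.72 | 0.80 |
| 4.0 | 2.80 | 0.69 | 0.73 | 0.82 | 0.91 |
| 4.5 | 3.15 | 0.78 | 0.82 | 0.92 | 1.02 |

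Example with limits 4.0 and 40%: WBC 3.0 with 30% neutrophils gives 3.0 × 0.30 = 0.90. WBC 3.0 is above 2.80 and 30% is above 26%, so neither flag fires.

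At the stopping level, WBC 1.6 with 30% neutrophils gives 0.48. The percentage flag misses this, but the WBC flag catches it. In general, the lowest unflagged count stays above 0.5 whenever 0.70 × 0.65 × (WBC LLN × neutrophil fraction LLN) exceeds 0.5, that is, when the product of the two limits exceeds 0.5 / 0.455 = 1.10. The smallest product assumed here is 3.5 × 0.38 = 1.33, so every count at or below 0.5 is flagged.

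**2. CRP with '<x' dropped**

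Assumptions: log-normal CRP, log SD 0.8 to 1.2, true active/placebo ratio 0.70, and 5% to 30% of placebo values NQ. The table gives active/placebo ratios from a simulation with 2,000,000 values per arm. Medians and means are shown because SAP Section 14.5.2 plans both.

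| NQ on placebo | NQ on active | Median ratio, '<x' dropped | Mean ratio, '<x' dropped | Median ratio, x/2 used |
|---|---|---|---|---|
| 5% | 9–12% | 0.74–0.75 | 0.73–0.74 | 0.70 |
| 10% | 16–20% | 0.77–0.78 | 0.75–0.76 | 0.70 |
| 20% | 29–35% | 0.81–0.82 | 0.78–0.80 | 0.70 |
| 30% | 41–47% | 0.84–0.85 | 0.80–0.82 | 0.70 |

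The median recovers under x/2 because fewer than half the values are NQ in either arm.

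For a low NQ fraction, the truncated log-normal mean gives E[log X | X > L] = mu + s·phi(z)/(1 − Phi(z)), with z = (log L − mu)/s. At 1% NQ on placebo and s = 1, z is −2.33 on placebo and −1.97 on active. The added terms are 0.027 and 0.059, so the geometric mean ratio is 0.70 × exp(0.059 − 0.027) = 0.72. At 0% NQ there is no bias.

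**The case against.** A reader might infer that the SAP hides neutropenia. The documents do not support that.

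- Counts at or below 0.5 trip a flag under the assumed limits. Appendix 9 of the protocol also requires them to be reported to the sponsor within 24 hours.
- The protocol's three cut-offs have different roles. Only 0.5 is a general on-study stopping level; 1.5 serves eligibility and restart, and 1.0 applies only after restart.
- Neutrophil counts are shown elsewhere: mean plots over time (Figures 3.4 and 3.5) and plots against exposure (Figures 5.2 and 5.4). The haematology change table includes minimum and maximum values. Clinically relevant laboratory changes are recorded as adverse events (Protocol Section 9.4.4), and a safety review team meets about every three months (Section 5.1).
- Other rows of the PCI table narrow the gap. When neutrophil % falls, other percentages must rise, and lymphocytes are flagged above 1.20x. Assume a lymphocyte upper limit of 45% and 12% other cells. The lymphocyte flag then fires above 54%, that is, at neutrophils below 100 − 54 − 12 = 34%. With a WBC limit of 4.0, the lowest wholly unflagged count becomes 2.80 × 0.34 = 0.95 rather than 0.73.

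The last point is fair, but 0.95 is still below both 1.0 and 1.5. The other displays do not fill the gap: means dilute isolated cases, and change tables do not count participants. Haematology is scheduled on treatment at Visits 5 and 10 and PK at Visits 6, 7 and 10, so only Visit 10 pairs a scheduled count with a trough.

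On NQ results, a reader might infer that '<x' values are lost to safety screening or that a harm is concealed. Neither follows. They are listed (Listings 31 and 58) and kept at half the limit for PCI assignment, and a low CRP is not a harm signal. CRP is summarised descriptively and is not a named endpoint. The protocol's abbreviations include high-sensitivity CRP, so few NQ values is plausible. Nor does the half-limit rule in the PK/PD figures prove a contradiction, since SAP Section 14.9.1.4 sets NQ drug concentrations to missing for population PK. What remains is an avoidable upward shift of unknown size.

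**Conclusion.** The point holds as a bounded reporting gap. The PCI screen looks at neutrophils only as a percentage, the protocol's rules are absolute counts, and no planned display counts participants by absolute count. With WBC limits of 3.5 to 4.5 and neutrophil limits of 38% to 50%, the lowest count that passes both flags is 0.61 to 1.02 ×10^9/L. Counts from there up to 1.5 can be unflagged, depending on how they divide between total white cells and percentage. The lymphocyte criterion may raise that floor to about 0.95 in the mid-range case. All these figures depend on normal ranges that the documents do not give.

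The CRP matter is secondary. The direction of the bias is clear, but its size depends on an NQ fraction that is not stated: negligible if few values are NQ, and a median ratio of up to 0.85 in place of 0.70 at 30% NQ on placebo.

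**What to change.** **Neutrophils.** Keep the percentage row in Section 14.8.1; replacing it would lose its 1.50x high flag. Add a summary of absolute neutrophil count by arm, at worst case post-baseline and by visit, with categories <1.5, <1.0 and ≤0.5 ×10^9/L. Add a matching participant listing. These are the protocol's existing cut-offs used as reporting categories only; no clinical rule changes.

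**CRP and fibrinogen.** In summaries and boxplots, set '<x' to x/2, as Section 14.6.4 already does for PCI assignment. Report the number of NQ values by arm and visit, so that the reader can judge how much the substitution matters.

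**Cost.** One added table and listing, one changed handling rule, and a rerun of the CRP and fibrinogen displays, all from data already collected. Half-limit substitution is approximate. The final tables will differ slightly in format from those of the strategic interim, which should be noted in the clinical study report.

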## 14.7. Appendix 7: Reporting Standards for Missing Data

### 14.7.1. Premature Withdrawals

Element	Reporting Detail
General	
 
Participant study completion (i.e. as specified in the protocol) was defined as completion of all phases of the study including the last study visit and the last scheduled procedure shown in the Schedule of Activities (Appendix 2).
 
For the purposes of reporting, a participant is considered to have completed the study if they have not withdrawn and attended Visit 10.
 
Withdrawn participants were not replaced in the study.
 
All available data from participants who were withdrawn from the study will be listed and all available planned data will be included in summary tables and figures, unless otherwise specified.
 
Data from the Early Withdrawal visit will not be included in any summaries or analyses except as part of a worst case post-baseline assessment.
 

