9.4.6. Spirometry Testing

Spirometry assessments will be obtained using spirometry equipment that meets or exceeds the minimal performance recommendations of the ATS/ERS [Miller, 2005]. All participants will have spirometry performed at Visits 1, 3, 7, 10 and where necessary Early Withdrawal. For each spirometry assessment, both pre- and post-bronchodilator measurements will be performed. For each FEV₁ and FVC determination, at least 3 acceptable spirometry efforts should be obtained. Acceptable spirometry efforts should have a satisfactory start of the test and end of the test (i.e. a plateau in the volume-time curve) and be free from artifacts due to cough, early termination, poor effort, obstructed mouthpiece, equipment malfunction, or other reasons. The largest FEV₁ and FVC from the 3 acceptable efforts should be recorded, even if they do not come from the same effort.

For each spirometry assessment, the following guidelines should be followed:

- Spirometry procedure conducted between 6:00 AM and 11:00 AM
- Where applicable, after completion of other visit assessments (e.g. participant questionnaires and blood collections)

- Short acting bronchodilators (i.e. rescue medications) should not be used for at least 4 hours prior to the spirometry assessment
- The morning dose of any inhaled maintenance treatment should be withheld until the completion of the spirometry assessment
- Participants should refrain from smoking for at least 1 hour prior to each spirometry assessment
- Participants should abstain from consuming beverages with high levels of caffeine (including tea and coffee) for at least 2 hours prior to each spirometry assessment

Post-Bronchodilator Spirometry Testing

- Following pre-bronchodilator spirometry assessment, post-bronchodilator spirometry is measured. Following measurement of pre-bronchodilator spirometry, post-bronchodilator spirometry is performed 15 ± 5 minutes after 4 puffs of short acting beta-agonist administered using a valved spacer (i.e. 100 µg per puff of salbutamol or albuterol; other short acting bronchodilators may also be used, e.g. ipratropium bromide, 4 x 40 µg) - according to the ATS/ERS guidelines.
- Similar to pre-bronchodilator spirometry testing, 3 acceptable spirometry efforts should be obtained and the highest FEV1 and FVC from the acceptable efforts should be recorded.

Additional details for the requirements and conduct of spirometry assessments are provided in the SRM.

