#### 8.4.4. Strategy for Intercurrent (Post-Randomization) Events

The intercurrent event of interest is treatment discontinuation. A ‘hypothetical’ strategy will be used to account for this event. All recorded data up to the time of treatment discontinuation will be included in the analysis. Subsequent data up to Day 168 will be assumed to be missing at random (MAR).

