#### 8.4.5. Statistical Analyses / Methods

##### 8.4.5.1. Frequentist MMRM Methodology Specification

Endpoint / Variables

 
Change from baseline in post-BD FEV1
 
Change from baseline in post-BD FVC
 

Model Specification

 
The following covariates will be included in the model: baseline, country, smoking status at screening, treatment, Visit, Visit *baseline and Visit *treatment interactions, where Visit is nominal. Visit will consist of two levels (Day 84 and 168), and treatment will consist of six levels (placebo and 5 active doses)
 
Two models will be fitted; one with a response variable (FEV1 or FVC), and one with a response variable of change from baseline (FEV1 or FVC).
 
An unstructured covariance structure for the R matrix will be used by specifying ‘type=UN’ on the REPEATED line.
 
The Kenward and Roger method for approximating the denominator degrees of freedom and correcting for bias in the estimated variance-covariance of the fixed effects will be used. If this method does not run, the residual method will be used instead
 
The OM option will be used to derive the least square (LS) means using coefficients which are based on the participants used in the analysis. The OM option requires an OM dataset which has a row for every participant-visit combination that contains all of the covariates used in the model and a macro variable containing the mean baseline for the participants used in the analysis.
 

Model Checking & Diagnostics

 
Distributional assumptions underlying the model used for analyses using MMRM will be examined by obtaining a normal probability plot of the residuals and a plot of the residuals versus the fitted values (i.e. checking the normality assumption and constant variance assumption of the model respectively) to gain confidence that the model assumptions are reasonable. Plots of residuals versus covariates and baseline versus response will also be examined.
 

Model Results Presentation

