### **14.3. Appendix 3: Assessment Windows**

In general, data will be reported according to the nominal time of clinic visits and assessments as specified in the protocol. For example, if a participant recorded values for the Day 28 visit that were actually made on the 21st day of treatment, they will be presented as Day 28 values in the summary tables.

Participants that withdraw from the study at the time of a scheduled study visit will have data collected in the eCRF as part of the scheduled study visit. In order to collect all questionnaires that are scheduled to be performed at the Early Withdrawal (EW) Visit, eDiary data is reported as an EW Visit. If the date of the EW diary assessment is the same as the date of a scheduled visit date from the eCRF and there is no diary data present at the scheduled visit in question, the EW diary data will be listed, summarized and analysed as part of the scheduled visit (if the diary data was scheduled to be performed at the visit in question).

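### The SAP's exclusion of Early Withdrawal data conflicts with its spirometry rule and leaves collected SGRQ and CAT values out of models that assume missing at random

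*SAP*

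**What the plan says.** The protocol's Schedule of Activities marks SGRQ-C, CAT and spirometry at Visit 3 (Day 1), Visit 7 (Day 84), Visit 10 (Day 168) and Early Withdrawal (EW). Spirometry is also done at screening. Protocol 9.4.6 confirms it: "All participants will have spirometry performed at Visits 1, 3, 7, 10 and where necessary Early Withdrawal".

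The SAP then handles EW data in several places:

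- **14.7.1** sets the general rule: "Data from the Early Withdrawal visit will not be included in any summaries or analyses except as part of a worst case post-baseline assessment". It also says "All available data from participants who were withdrawn from the study will be listed", and Appendix 11 plans SGRQ and CAT listings.
- **14.3** makes an exception for withdrawal at a scheduled visit. Such participants "will have data collected in the eCRF as part of the scheduled study visit". If a questionnaire entered as EW has the same date as a scheduled visit, that visit has no diary data and the assessment was due there, then "the EW diary data will be listed, summarized and analysed as part of the scheduled visit".
- **8.4.4**, for spirometry only, says: "All recorded data up to the time of treatment discontinuation will be included in the analysis". Later data are assumed missing at random (MAR). The model in 8.4.5.1 has two visit levels, Day 84 and Day 168.
- **7.2.4** analyses SGRQ and CAT with the E-RS longitudinal method. The data rule in that section (7.1.3.4) and the responder rule (7.2.3.4) restrict analysis to data from before a relevant deviation or treatment discontinuation, with later data assumed MAR.

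**The concern.** These three measures have only two scheduled post-baseline visits. A participant who stops before Day 84, on a day that is not a scheduled visit, gives the trial one post-baseline value of each, at EW, and 14.7.1 keeps it out of the models. A participant who stops between Day 84 and Day 168 keeps the Day 84 value but loses the one closest to withdrawal.

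Two things are at stake. For spirometry, a programmer cannot follow both 8.4.4 and 14.7.1 as written. For SGRQ and CAT, MAR is more credible when the last on-treatment observation is in the model, and here it is left out. SGRQ total score is a key secondary endpoint in the protocol synopsis, and the SAP specifies no sensitivity analysis of the MAR assumption for SGRQ or CAT.

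**Working it through.** **1. Does the exception inside 14.7.1 help?** No. SAP 14.6.4 defines maximum, minimum and worst-case post-baseline assessments for laboratory, ECG and vital-sign data. It defines none for SGRQ, CAT or spirometry.

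**2. Does 14.3 help?** In part. It keeps values when withdrawal coincides with a scheduled visit. For questionnaires the assessment must be due at that visit, so for SGRQ and CAT this means Day 84 or Day 168. If withdrawals were spread evenly over 168 days, about 60 × 7/168 = 2.5 would fall within the protocol's ±3-day window around Day 84. The number would be larger if people tend to withdraw at clinic visits.

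**3. Is an EW value recorded by the time of discontinuation?** The SAP does not say so directly, but its text leans that way. The introduction to Section 7 says nothing was scheduled for collection after study treatment was discontinued, and EW is a scheduled collection. SAP 14.4.1.4 counts unscheduled spirometry, CAT and SGRQ values as on-treatment up to the treatment stop date plus 3 days. SAP 14.6.1 uses the EW date as one candidate for a missing stop date.

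**4. Is there a contradiction?**

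| Measure | Rule on data used | Does 14.7.1 contradict it? |
|---|---|---|
| Spirometry | 8.4.4: everything recorded up to discontinuation | Yes, for an EW value recorded by then. 8.4.5.1 offers no place for it |
| SGRQ, CAT change | 7.1.3.4 via 7.2.4: nothing after deviation or discontinuation | No. The rule sets a limit and does not promise to use everything before it |
| SGRQ, CAT responders | 7.2.3.4: same form of limit | No |

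**5. How many participants?** Inputs from protocol 5.2 are 600 randomized and 10% dropout. The plan's own figure is reproduced: 600 × (1 − 0.10) = 540 completers. That leaves 600 − 540 = 60 withdrawers, or 60/6 = 10 per arm.

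The documents give no timing, so the share leaving before Day 84 is an assumption. So is attendance of every such participant at an off-schedule EW visit.

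| Share before Day 84 (assumed) | No post-baseline value in the models | % of 600 | Contributors |
|---|---|---|---|
| 25% | 60 × 0.25 = 15 | 2.5% | 585 |
| 50% (even spread: 84/168) | 60 × 0.50 = 30 | 5.0% | 570 |
| 75% | 60 × 0.75 = 45 | 7.5% | 555 |

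The remaining 45, 30 or 15 withdrawers keep Day 84 and lose only the later EW value. SGRQ and CAT are analysed in the per-protocol population, so actual counts there will be somewhat lower.

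**6. What could it do to a treatment difference?** Let p be the proportion withdrawing in an arm and D the worsening in its withdrawers beyond what the model predicts. The shift in the difference is roughly p(active) × D(active) − p(placebo) × D(placebo). With the same D in both arms, in absolute size:

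- 10% vs 10% dropout: (0.10 − 0.10) × D = 0 for any D.
- 5% vs 15% dropout: 0.10 × 2 = 0.2, 0.10 × 4 = 0.4 and 0.10 × 8 = 0.8 units for D = 2, 4 and 8.

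Both p and D are assumed. For scale, the SAP's SGRQ responder threshold is 4 units, so 0.8 is one fifth of it.

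**The case against.** The strongest reply has four parts.

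**The contradiction is narrow.** A reader might infer that 14.7.1 breaks a stated rule for SGRQ and CAT as well. It does not: the inclusive sentence sits in the spirometry section alone. This part of the reply stands in full.

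**The data are not discarded.** A reader might infer from 14.7.1 that EW values vanish. They are listed, and 14.3 retains those taken at a scheduled visit. This also stands. What is lost is the use of off-schedule values in the models.

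**Assigning every EW value to the next visit would be poor practice in the main model.** A Day 10 reading would be labelled Day 84 (84 − 10 = 74 days early) and a Day 90 reading Day 168 (78 days early). That resembles carrying an early observation forward and fits badly with a hypothetical strategy aimed at the outcome had treatment continued. This stands as an argument against unrestricted assignment. It does not count against a bounded window, or against using distant values in a sensitivity analysis. SAP 14.3 already accepts some displacement: its example reports a visit made on day 21 as Day 28.

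**The size is mostly assumed, and the primary analysis is safe.** Only 600 and 10% come from the documents. Protocol 8.3 provides for participants lost to follow-up, who may never attend EW. An EW visit after the last dose might also fall outside 8.4.4. These points limit the size; they do not remove the mismatch between 8.4.4, 8.4.5.1 and 14.7.1. Rewording 8.4.4 alone would clear the contradiction but leave collected on-treatment values unused.

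**Conclusion.** The point holds in a limited form. For spirometry, 14.7.1 and 8.4.4 cannot both be followed where an EW value was recorded by discontinuation, and 8.4.5.1 does not say where it would go. For SGRQ and CAT there is no contradiction. There is a loss of collected on-treatment information from MAR models, one of which serves a key secondary endpoint.

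The reach is 15 to 45 participants, given 10% dropout, 25% to 75% of withdrawals before Day 84, and all of those attending an off-schedule EW visit. The documents do not support a claim of bias of any particular size. The illustration runs from 0 to 0.8 units, and it is zero when dropout and withdrawers' outcomes are balanced. Nor do they support extending the point to the primary endpoint: the Month 6 E-RS score comes from daily diary entries and does not use EW clinic assessments.

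**What to change.** Qualify the sentence in SAP 14.7.1 and align it with 8.4.4 and 8.4.5.1. State a window within which an on-treatment EW value (up to stop date + 3 days, as 14.4.1.4 already uses for unscheduled visits) is assigned to Day 84 or Day 168 when that visit has no value. Set the width before the final analysis, and apply it to SGRQ, CAT and spirometry.

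Add a sensitivity analysis of the SGRQ, CAT, responder and spirometry endpoints that includes all on-treatment EW values, including those outside the window.

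The cost is SAP wording, a derivation rule and a few extra displays, with no new data collection. The downside is that assigned values are off the nominal day, which is why values far from the visit belong only in the sensitivity analysis.
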